The IAU aims to estimate the average treatment effect for the treated (ATT). Once matched controls have been selected, the IAU will estimate the effect of ICTs on the intervention group compared with the control group by fitting multivariable regression models, both unadjusted and adjusted for covariates. The adjusted model will contain all variables that were used in the matching process to adjust for any remaining observed imbalance, as well as any other covariates predictive of outcome. Index date will be included as a quarter/year categorical variable. Modelling checks for collinearity will be carried out and, if appropriate, the list of covariates will be changed accordingly.

Explored modelling options will include multilevel models with locality as a random effect, to capture any between-locality heterogeneity in outcomes. An additional advantage of a random effect modelling approach lies in obtaining more precise local estimates in the event of issues with data sparsity from particular localities.

Each outcome will be analysed by fitting a regression model that is appropriate to the type of outcome and the distributional properties of the data.

The count variable endpoints, such as number of emergency admissions per patient, will be analysed using a generalised linear model suitable for count data, such as a Poisson, to estimate the rate ratio between intervention and matched control patients. The effect of the intervention on the absolute (as opposed to relative) number of events (e.g. admissions) will also be estimated.

Model fit will be assessed by examining diagnostic statistics and over-dispersion parameters (e.g. the ratio of the residual deviance to the residual degrees of freedom), and excess zeros by comparing predicted and observed proportion of zero counts. If over-dispersion is detected then an alternative model, such as a negative binomial or the zero-inflated Poisson for count data, will be fitted. Where a similarly good fit is obtained using multiple models, a choice will be made by comparing the log-likelihood ratio and the Akaike information criterion (AIC), as appropriate. The appropriateness of the random effect assumption on locality will be assessed through formal statistical checks (like the intraclass correlation coefficient) and comparison with the corresponding fixed effect model.

As a guide, Table 6 details the typical regression models and alternatives for each outcome.

Table 6. Regression models for each outcome

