Type of endpoint	Outcome	Initial model	Alternative model	Diagnostics
Count data	Number of admissions / A&E attendances/outpatient visits	Poisson	Negative binomial / Zero-inflated Poisson	Over-dispersion Model fit Excess zeros
Proportions	Proportion of emergency/elective bed days (of whole follow-up period)/ Proportion of deaths in hospital/ Proportion of patients who die (sensitivity analysis)	Binomial	Quasi-binomial/Negative binomial	Model fit Distribution of model residuals Over-dispersion Heteroscedasticity diagnostics

To account for differing attrition arising from death, moving away from the area or different entry dates into the study, an offset of the number of days in the study will be added to the model. However, the offset assumes that the number of days that are ‘missing’ is random and that the rate of outcomes, for instance emergency admissions, is constant, when in fact this is unlikely to be the case. For example, a patient may use more hospital services in the final months of life. The IAU will examine the length of time people were followed up in the study and reasons for leaving the study between the groups. As detailed in the section on Index dates and follow-up period (p. 23), a patient’s follow-up period ended (was censored) when the patient either died, moved away from NEHF or the study period ended. If the length of time patients were followed up in the study or the reasons for leaving the study differed between the groups, the IAU will consider doing an alternative analysis as a sensitivity analysis.

Subgroup analysis

As the localities have differed in how they implemented the ICTs and which patients they targeted, as well as in what other interventions they offered outside of the ICTs (see Table 1), the IAU will aim to do a subgroup analysis by locality. However, there is a risk that the data are so sparse in some localities that models cannot be fitted in those localities. If the models can be fitted, the results are unlikely to show statistically significant results due to small sample sizes; however, a comparison between localities may nonetheless provide learnings to NEHF as to whether the effect is homogenous across sites and if not, which locality may be showing most potential.

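### For sparse counts the only over-dispersion measure the plan names, residual deviance over degrees of freedom, can look reassuring despite real over-dispersion, so Poisson may be kept with standard errors that are too small

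*Protocol*

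**What the plan says.** In the Protocol, section 2 (Methods), Statistical analysis, the count endpoints "will be analysed using a generalised linear model suitable for count data, such as a Poisson, to estimate the rate ratio". Fit is to be judged with diagnostic statistics and measures of over-dispersion, the example given being "the ratio of the residual deviance to the residual degrees of freedom", and the same sentence adds "excess zeros by comparing predicted and observed proportion of zero counts". The rule for leaving Poisson follows: "If over-dispersion is detected then an alternative model, such as a negative binomial or the zero-inflated Poisson for count data, will be fitted". Where several models fit about equally well, "a choice will be made by comparing the log-likelihood ratio and the Akaike information criterion (AIC), as appropriate".

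Table 6, offered as a guide, repeats Poisson as the initial count model, with negative binomial and zero-inflated Poisson as alternatives and the diagnostics "Over-dispersion Model fit Excess zeros". A quasi-likelihood option appears for proportions but not for counts, and robust standard errors are not mentioned. The Addendum (section 5) changes covariate selection and drops the multilevel model, but leaves this check as it was.

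**The concern.** The deviance ratio is usually read against 1. That reading needs mean counts that are not small. When most patients have no event, the expected deviance per patient falls well below 1 even if Poisson is exactly right. A moderate amount of over-dispersion then moves the ratio from one value under 1 to another value under 1, and an analyst reading it the usual way sees no reason to change model.

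This matters most for chronic ambulatory care sensitive and urgent care sensitive admissions. Both are primary outcomes and both are subsets of emergency admissions. The protocol looks to ambulatory care sensitive admissions to separate avoidable admissions from those due to unmet need. The Addendum concedes few events for some outcomes, without naming them. The ratio depends on the mean count per patient, not on the number of patients, so a locality or mental-health subgroup with the same rate has the same difficulty. If Poisson is kept wrongly, confidence intervals are too narrow and p values too small.

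**Working it through.** The protocol gives no event rate or dispersion figure, so there is no stated result to reproduce. The check asks how the named ratio behaves over a range of assumed rates.

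**Inputs from the protocol.** About 900 intervention patients (Statistical conclusion validity); 1:1 matching (Identifying control group); follow-up of 1 to 23 months with a time offset (Study endpoints); 95% confidence intervals (Reporting).

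**Assumptions.** Follow-up *t* is uniform on 1 to 23 months, so E[t] = 1 year and E[t²] = 1 + (22/12)²/12 = 1.280. There is no treatment effect and the fit is an unadjusted two-group Poisson. Counts follow a gamma-Poisson distribution with variance μ + aμ², where μ = rate × t and *a* is the frailty variance.

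**Step 1: reference value of the ratio.** For one patient the expected Poisson deviance is 2·E[y·log(y/μ)]. At a fixed mean of 0.2 the terms are:
- y = 1: 0.1637 × 1.609 = 0.264
- y = 2: 0.0164 × 4.605 = 0.075
- y = 3: 0.0011 × 8.124 = 0.009

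The sum is 0.348 (0.349 with the remaining terms), and doubling gives 0.70. Averaged over the spread of follow-up at 0.2 per year it is 0.65. So 0.65, not 1, is the value for a correct model.

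**Step 2: Pearson ratio.** E[(y − μ)²/μ] = 1 + aμ, which averages 1 + a × rate. Its reference value is 1 at every rate. At 0.2 per year and a = 2 it is 1 + 2 × 0.2 = 1.40.

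**Step 3: standard error and type I error.** True variance over Poisson variance of a group's total is 1 + a × rate × E[t²]/E[t]. At 0.2 per year and a = 2 this is 1 + 2 × 0.2 × 1.280 = 1.512, so the true standard error is √1.512 = 1.23 times the Poisson one. Type I error is 2·[1 − Φ(1.96/1.23)] = 11%.

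**Step 4: over the range.**

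| Rate/year | a | Deviance/df | Pearson/df | Zeros observed / predicted | True SE / Poisson SE | Type I error |
|---|---|---|---|---|---|---|
| 0.05 | 0 | 0.29 | 1.00 | 95.2% / 95.2% | 1.00 | 5% |
| 0.05 | 4 | 0.30 | 1.20 | 95.7% / 95.2% | 1.12 | 8% |
| 0.1 | 0 | 0.45 | 1.00 | 90.6% / 90.6% | 1.00 | 5% |
| 0.1 | 2 | 0.48 | 1.20 | 91.6% / 90.6% | 1.12 | 8% |
| 0.1 | 4 | 0.50 | 1.40 | 92.3% / 90.6% | 1.23 | 11% |
| 0.2 | 0 | 0.65 | 1.00 | 82.3% / 82.3% | 1.00 | 5% |
| 0.2 | 2 | 0.75 | 1.40 | 85.3% / 82.3% | 1.23 | 11% |
| 0.2 | 4 | 0.82 | 1.80 | 87.1% / 82.3% | 1.42 | 17% |
| 0.3 | 2 | 0.97 | 1.60 | 80.3% / 75.0% | 1.33 | 14% |
| 0.4 | 1 | 1.04 | 1.40 | 73.1% / 68.5% | 1.23 | 11% |
| 0.4 | 4 | 1.38 | 2.60 | 80.2% / 68.5% | 1.75 | 26% |

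Simulation with 900 per group agrees: type I error of about 10% to 17% at 0.2 per year and 9% to 11% at 0.1 per year for a = 2 to 4. Robust standard errors bring it back to about 5%. In 400 simulated datasets per setting at 0.1 and 0.2 per year with a of 1 or more, AIC preferred the negative binomial in 92% to 100% when it was fitted.

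**Step 5: zero-inflated option.** With zero-part probability p in each group, the overall rate ratio is [(1 − p₁)/(1 − p₀)] × the count-part ratio. The two agree if group is not in the zero part and differ otherwise. The protocol does not say which specification it would use.

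**The case against.** A reader might infer that Poisson will be kept and that the primary results will therefore be wrong. The document does not support that, for five reasons.

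- **The ratio is only an example.** No threshold is attached, and Pearson chi-square/df would fit the wording equally well. This stands. Still, the deviance ratio is the only measure named, and it is the weaker one for sparse outcomes.
- **There is a second check.** In simulations with 850 per group, the gap between observed and predicted zeros averaged 9.1 and 14.9 standard deviations at 0.2 per year (a = 2 and 4), and 5.3 and 9.3 at 0.1 per year. So the plan's full set of checks does carry the signal. But the plan does not say to standardise the gap and gives no cut-off. The raw gap at 0.1 per year and a = 2 is one percentage point, and the switching sentence refers to over-dispersion, not to zeros.
- **AIC and full reporting of tested models** (Sensitivity analyses) help once an alternative has been fitted. The text requires one only after over-dispersion is detected.
- **Rarity is not shown.** The cohort is mostly elderly and needs an admission in the previous three years. At 0.4 per year with a of 2 or more the ratio gives a usable signal (1.17 to 1.38).
- **The fits are unadjusted.** The planned covariates include prior admissions and comorbidities, which would absorb some frailty. Residual variance of 2 to 4 is an assumption.

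A reader might also infer that zero-inflated Poisson necessarily changes the estimand. It does so only if group enters the zero part, which the plan leaves open.

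**Conclusion.** The point holds conditionally. Residual deviance over degrees of freedom is a poor choice of named check for sparse counts, because its reference value is well below 1 and it can stay below or near 1 with real over-dispersion. That applies at about 0.3 events per year or less, and at 0.4 per year when over-dispersion is moderate. If the check is relied on there and Poisson is kept, true standard errors are about 12% to 42% larger than reported at 0.1 to 0.2 per year with frailty variance 2 to 4. The matching type I error is 8% to 17% instead of 5%. At 0.05 per year the harm is smaller (up to 8%).

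These sizes rest on assumed rates, gamma frailty, uniform follow-up and no covariate adjustment. The document does not give the rates of the two condition-specific primary outcomes, so whether they fall in this range is unknown. This is an inexpensive improvement worth making, not evidence that the results are wrong.

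**What to change.** - Make negative binomial, or Poisson with robust standard errors, the default for every count outcome, including subgroups. Cluster by patient if a control is used more than once, which the matching section allows.
- Replace the deviance ratio as the named measure with Pearson chi-square/df or a likelihood-ratio test of Poisson against negative binomial. Pearson chi-square/df is itself noisy at the lowest rates: at 0.05 per year it passed 1.1 in 14% of correctly Poisson datasets. That is a further reason to set the default first and use the statistic as description.
- If a zero-inflated model is used with group in the zero part, report the overall (marginal) rate ratio.

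The cost is two or three sentences and a model option. Intervals widen where over-dispersion is present, roughly by the standard-error ratio in the table, and hardly change where it is absent.

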The results of all tested regression models will be presented in the technical appendix to the report, to show if the effect size and significance of the selected best model were sensitive to the choice of model.

Sample size calculation

No sample size was calculated for this study. The analysis is considered informative and will be carried out regardless of whether our study population is of a sufficient size to detect a statistically significant difference.

3. Limitations and sources of bias

Threats to validity

Internal validity

One of the main threats to the validity of this study is unobserved confounding. Unobserved confounding can occur at area, hospital, general practice or patient level. There is always a risk of unobserved confounding in non-randomised studies, but here the risk is larger due to the way patients have been selected for the ICTs, especially up to June 2017 when patients were primarily selected based on clinical judgement. This leads to potential selection bias. The majority of referrals come from GPs, though referrals are also received from other health care workers (e.g. community staff, mental health, social care).¹⁰ The lack of information on any non-clinical reasons for referring patients (for example, a close family member dying or moving away), together with a lack of primary care and community data, makes it difficult for us to identify what characteristics the referred patients were selected on and therefore to identify a matched control group that is similar to the intervention group in these characteristics. The uncertainty of the results due to potential unobserved confounding will not be reflected in the confidence intervals or p values, as these capture other kinds of uncertainties. Therefore, even a statistically significant result will need to be interpreted with caution. The IAU will perform some sensitivity analysis (see section on Sensitivity analysis, p. 31) to try to assess the presence of unobserved confounding.

If important predictive covariates are omitted from the matching and regression models, then unobserved differences between the groups may contribute to any or part of any difference in outcomes. These differences would in turn then erroneously be attributed to the intervention.

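### A zero-inflated Poisson may be selected for count outcomes, but the plan does not say how its two parts give the rate ratio it sets out to estimate

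*Protocol*

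**What the plan says.** Protocol, section 2, Statistical analysis: "The IAU aims to estimate the average treatment effect for the treated (ATT"). Count endpoints are to be analysed with a model such as a Poisson "to estimate the rate ratio between intervention and matched control patients", with time in the study as an offset. An absolute effect is added without a method: "The effect of the intervention on the absolute (as opposed to relative) number of events (e.g. admissions) will also be estimated".

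The same section checks over-dispersion and "excess zeros by comparing predicted and observed proportion of zero counts". It continues: "If over-dispersion is detected then an alternative model, such as a negative binomial or the zero-inflated Poisson for count data, will be fitted". Where several models fit about equally well, "a choice will be made by comparing the log-likelihood ratio and the Akaike information criterion (AIC), as appropriate". Table 6, offered as a guide, gives the alternative for admissions, A&E and outpatient counts as "Negative binomial / Zero-inflated Poisson".

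Under Sensitivity analyses, results of every model tried go into the technical appendix, "to show if the effect size and significance of the selected best model were sensitive to the choice of model". The reporting section asks for effect measures with 95% confidence intervals and p values, a forest plot of adjusted results, and an unadjusted table with event counts and exposure time by group.

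No section, including the July 2018 addendum, says whether treatment enters the zero part of a ZIP, which ZIP parameter is reported, or how the two parts are turned into a rate ratio.

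**The concern.** Poisson and negative binomial treatment coefficients are both log ratios of the overall event rate. A ZIP splits patients into an always-zero class and the rest, and its count coefficient compares rates only among the rest. A difference between groups in the share who can have an event goes into the zero part. Moving from negative binomial to ZIP on fit can therefore change the question as well as the variance model, and the appendix comparison of effect size and significance would then set unlike quantities side by side.

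Four of the five primary outcomes are counts, as are readmissions, elective admissions and outpatient attendances among the secondary ones. The addendum reports few events for some outcomes, so the excess-zero check may well matter. The care teams aim to reduce emergency admissions, and the protocol allows that proactive case finding may raise them in the short term. Either could change how many patients are admitted at all.

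**Working it through.** The plan states no event rate, zero share, dispersion or power, so there is no figure of its own to reproduce.

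**Algebra.** Let π be the always-zero share and λ the rate per year among the rest (1 = intervention, 0 = control). The group mean rate per person-time is (1 − π)λ, so

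group rate ratio = [(1 − π1)/(1 − π0)] × exp(β),

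where β is the ZIP count coefficient. exp(β) equals the group rate ratio only when π1 = π0.

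**Inputs from the protocol.** About 900 intervention patients (Statistical conclusion validity); 1:1 matching (Identifying control group); follow-up of 1 to 23 months with a time offset (Primary outcomes); 95% level, taken as two-sided because sidedness is not stated.

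**Assumed inputs.** Rates of 1 or 2 events per person-year, always-zero shares of 0.30 and 0.405, uniform follow-up, no covariates.

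- Scenario A: zero share 0.30 in controls and 0.405 in the intervention group, same rate among the rest. Group ratio = 0.595/0.70 = 0.85; exp(β) = 1.
- Scenario B: zero share 0.405 in controls and 0.30 in the intervention group. At 1 event per person-year, λ0 = 1/0.595 = 1.681 and λ1 = 1/0.70 = 1.429. Group ratio = (0.70 × 1.429)/(0.595 × 1.681) = 1.00; exp(β) = 1.429/1.681 = 0.85.
- Scenario E: zero share 0.30 in both groups, group ratio 0.85.

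Results from 600 replicates per scenario, as median ratio and percentage rejecting:

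| Scenario | ZIP count coefficient, treatment in both parts | ZIP, treatment in count part only | Negative binomial | Poisson, robust SE |
|---|---|---|---|---|
| A, 2/year, true 0.85 | 1.00, 5.2% | 0.975, 12% | 0.85, 81% | 0.85, 86% |
| A, 1/year, true 0.85 | 1.00, 5.7% | 0.926, 32% | 0.85, 69% | 0.85, 73% |
| B, 1/year, true 1.00 | 0.85, 82% | 0.914, 41% | 1.01, 3.7% | 1.01, 4.7% |
| B, 2/year, true 1.00 | 0.85, 99.8% | 0.866, 99% | 1.00, 1.5% | 1.00, 4.3% |
| E, 1/year, true 0.85 | 0.85, 73% | 0.85, 83% | 0.845, 75% | 0.847, 78% |

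AIC preferred ZIP to negative binomial in every run of A, B and E. That is expected, because the data were generated from a ZIP. Scenario E shows no mismatch when the zero shares are equal.

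**When is ZIP selected?** Gamma heterogeneity was added to similar scenarios with 750 per group. In one, the share at risk falls from 60% to 48% (ratio 0.48/0.60 = 0.80). In the other, 50% × 2.0 is set against 60% × 1.67 per year (ratio 1.00).

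- Variance 0.3: AIC chose ZIP in 63% and 71% of runs. A separate run with 900 per group gave 19% to 43%, so the frequency depends on the settings.
- Variance 0.6: 0% and 0.7%, and 13% in the first scenario at half the event rate. The run with 900 per group gave about 0%.
- Variance 1.0 and 1.5: 0%.

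With negative binomial data and no structural zeros, AIC chose ZIP in 0% of runs. A ZIP used there without that comparison rejected a true null in 19% to 39% of runs, against 3.5% to 6.7% for negative binomial.

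**The case against.** The strongest reply is that the error is not on the page. A reader might infer that the plan makes the ZIP count coefficient its headline test. It does not say so. It names the rate ratio between the groups as the target, and the promised absolute effect would, after a ZIP, normally come from predicted means that use both parts. This stands: the fault is a missing step between a permitted model and the stated measure.

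A reader might also infer that a real fall in admissions will be missed or a false one declared. The documents do not support that. The large figures come from data built with 30% to 40.5% always-zero patients and no other heterogeneity. Every included patient had an admission in the previous three years and most of those referred are older with complex needs, so a large never-at-risk class is doubtful for all-cause emergency admissions or A&E attendances. With more heterogeneity, AIC moves to negative binomial. This also stands, and it limits how often harm would occur.

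The table of events and exposure time lets anyone compute a crude rate ratio, and the appendix would show a Poisson or negative binomial fit that disagreed with a ZIP. These soften the problem. They do not correct the adjusted ratio, its interval and p value, or the forest plot.

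That such detail belongs in a separate analysis plan carries little weight. The document calls itself the statistical analysis protocol and sets out to fix the methods in detail before data access.

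**Conclusion.** The point holds in a conditional form. The plan names a group rate ratio for count outcomes and permits a model whose count coefficient is not that ratio unless the always-zero shares are equal, with no step that links the two. The algebra needs no assumption about the data.

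Harm needs three things together: ZIP is selected, which is likely with strong structural zeros and little other heterogeneity; the zero share differs between groups; and the count coefficient is reported as the rate ratio. If all three occur, the simulations give about 5% detection of a true ratio of 0.85 where a rate-based test has 69% to 86% power, and 82% or more false rejection in the offsetting case with treatment in both parts. Event rates, zero shares and heterogeneity are all assumed, since the document gives none. Nothing in it shows that a ZIP was selected for any outcome. The point merits a clear correction to the text and does not show that any result is wrong.

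**What to change.** In Statistical analysis and Table 6, state that the overall rate ratio per person-time is the reported and tested quantity for every count outcome, whichever model fits best. Take it from a negative binomial model or from a Poisson model with robust standard errors.

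If a ZIP is fitted, do not report its count coefficient as the rate ratio. Predict each intervention patient's mean count from both parts, once as treated and once as control, at that patient's own follow-up time. Report the ratio of the two sums:

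Σ(1 − π1i)λ1iTi / Σ(1 − π0i)λ0iTi,

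with a bootstrap or delta-method confidence interval. Averaging over intervention patients matches the ATT aim, and the same predictions give the absolute effect.

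Under Sensitivity analyses, compare models in the appendix on this common ratio. Because the addendum was written after the analysis, it should also say whether any reported count result came from a ZIP; if so, that result should be re-expressed this way.

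The cost is a few sentences and one extra analysis step where ZIP is used. The overall ratio does not separate having any admission from the number of admissions; the two ZIP parts can still be shown descriptively.

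### Table 6 lists an over-dispersion check and quasi-binomial/negative binomial alternatives for two yes/no death outcomes, where the check reflects only the event share and the negative binomial is not a valid model

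*Protocol*

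**What the plan says.** The protocol's Statistical analysis section and its Table 6 set the models by type of endpoint.

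- The Proportions row covers emergency and elective bed days as a share of follow-up, and also "Proportion of deaths in hospital/ Proportion of patients who die (sensitivity analysis"). The initial model is binomial, the alternatives are "Quasi-binomial/Negative binomial", and over-dispersion is among the listed diagnostics.
- The text above the table says that fit will be judged by diagnostic statistics and "over-dispersion parameters (e.g. the ratio of the residual deviance to the residual degrees of freedom"). It gives no cut-off.
- The switching rule is: "If over-dispersion is detected then an alternative model, such as a negative binomial or the zero-inflated Poisson for count data, will be fitted".
- For models that fit about equally well, "a choice will be made by comparing the log-likelihood ratio and the Akaike information criterion (AIC), as appropriate".
- The table's status is stated: "As a guide, Table 6 details the typical regression models and alternatives for each outcome".
- The Sensitivity analyses section adds: "The results of all tested regression models will be presented in the technical appendix to the report".

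Under Study endpoints, place of death is a secondary outcome built from hospital deaths among all deaths, which is one yes/no per deceased patient. Under Sensitivity analyses, all-cause mortality is a check on unobserved confounding, alongside Kaplan-Meier estimates. The July 2018 addendum does not change this row of Table 6.

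**The concern.** The row mixes two kinds of data. A bed-day proportion is nights out of days for each patient. Nights cluster into stays, so extra-binomial variation is expected, and a check with a quasi-binomial fallback makes sense. Place of death and death are single 0/1 values per patient. Once the mean p of such a value is fixed, its variance is p(1 − p), and independent ungrouped records hold no information about extra variation. A negative binomial also allows counts above 1, so it does not describe a yes/no outcome.

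The practical risk is a false alarm. The one statistic named as an example does not centre on 1 for 0/1 data. An analyst who read a value of 1.2 to 1.4 as over-dispersion could replace a sound logistic model with one whose intervals are too wide, and report a rate ratio where an odds ratio was expected. Place of death is the plan's only end-of-life outcome and is analysed only among those who die, so precision is already limited.

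**Working it through.** The protocol gives no death rate, hospital-death share or sample size calculation, so it has no figure to reproduce. The inputs are about 900 intervention patients (Statistical conclusion validity), 1:1 matching (Identifying control group), 95% confidence intervals (Reporting), and an event share p that has to be assumed.

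**Step 1: the named ratio under a correct logistic model.** A record contributes −2 ln p to the deviance if the event occurs and −2 ln(1 − p) if not. The expected deviance/df is therefore −2[p ln p + (1 − p) ln(1 − p)]. At p = 0.45 this is −2[0.45 × (−0.799) + 0.55 × (−0.598)] = 1.38. The Pearson version averages (y − p)²/[p(1 − p)], which is 1 for every p.

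**Step 2: the negative binomial.** Fitted to 0/1 data, its dispersion estimate goes to zero (0.00005 in one test fit), which leaves a Poisson model. Poisson takes the variance to be p when it is p(1 − p), so the model-based standard error of the log ratio is too large by √{p/[p(1 − p)]} = 1/√(1 − p).

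**Step 3: the quasi-binomial.** The binomial standard error is multiplied by √φ. With φ from Pearson/df the factor is 1. With φ from deviance/df it is the square root of the step 1 value.

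| assumed p | deviance/df | negative binomial SE factor | quasi-binomial SE factor, deviance scaling |
|---|---|---|---|
| 0.10 | 0.65 | 1.05 | 0.81 |
| 0.15 | 0.85 | 1.08 | 0.92 |
| 0.20 | 1.00 | 1.12 | 1.00 |
| 0.30 | 1.22 | 1.20 | 1.11 |
| 0.40 | 1.35 | 1.29 | 1.16 |
| 0.45 | 1.38 | 1.35 | 1.17 |
| 0.50 | 1.39 | 1.41 | 1.18 |

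Below p = 0.2 the deviance-scaled factor is under 1, but there the ratio would not have signalled over-dispersion.

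**Step 4: simulation.** Each setting had 400 runs, no treatment effect and one covariate, with 1,800 records for p = 0.1 to 0.4 and an assumed 360 deaths for p = 0.4 to 0.5.

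- Deviance/df from the correct logistic model exceeded 1 in 0% of runs at p = 0.1, 37% at 0.2 and 100% at 0.3 and above. Pearson/df was 1.00 to 1.01 throughout.
- The Poisson-limit standard error was 1.07 times the robust one at p = 0.1, 1.33 at 0.4 and 1.45 at 0.5, slightly above the closed form because of the covariate.
- Two-sided type I error was 3% to 6% for logistic regression, and 1% to 1.5% for the Poisson limit at p = 0.3 to 0.45.
- AIC preferred the binomial to the Poisson-limit fit in every run.

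**Step 5: which outcome is exposed.** The ratio passes 1 at p of about 0.2. For death that means more than about 0.2 × 900 = 180 deaths per group. An assumed 90 deaths per group would be 90/900 = 10% mortality, with a ratio of 0.65 and no alarm. For place of death, p is the hospital share among deaths, and any share from 0.3 to 0.5 gives a ratio of 1.22 to 1.39.

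**The case against.** The strongest reply is that nothing compels the switch. Table 6 is offered as a guide, and the text asks for a model suited to the type of outcome, which on a sensible reading excludes a negative binomial for a yes/no variable. The initial model is already binomial. The switching sentence names its examples for count data, deviance/df is only an example, and quasi-binomial is listed before negative binomial. AIC would pick the binomial where it is used, and the commitment to report every tested model would expose a switch. The error would be conservative and would touch no primary outcome.

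Most of this stands, and it limits the point to a possible misstep. It does not remove the defect. Table 6 is the protocol's only outcome-specific model list, and it names an unsuitable model and an uninformative check for two named outcomes. The likelihood and AIC step applies "Where a similarly good fit is obtained using multiple models, a choice will be made by comparing the log-likelihood ratio" and AIC. On deviance/df the binomial can look poor (1.38 at p = 0.45) while the Poisson limit does not (−2p ln p = 0.72), so that step need not be reached. Quasi-binomial has no likelihood and hence no AIC. Reporting all models helps the reader afterwards but does not correct the selection rule.

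A reader might also infer that over-dispersion cannot exist in these data at all. That is too strong. The Identifying control group section allows one control patient to be matched several times with different index dates, so records may be correlated. A negative binomial would not deal with that either.

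**Conclusion.** The point holds as a specification error of modest consequence. For independent 0/1 records the over-dispersion diagnostic carries no information, and its example form exceeds 1 once p is above about 0.2 even when the logistic model is right. A switch to negative binomial would widen standard errors by about 5% at p = 0.1 to 41% at p = 0.5. A switch to quasi-binomial would add nothing with Pearson scaling and at most about 18% with deviance scaling. All these sizes rest on assumed event shares.

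Three stronger readings are not supported:

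- **A single figure such as 30% excess width.** This needs an event share near 0.41, which the protocol does not give.
- **That the mortality check on confounding is undermined.** If mortality is below about 20% the ratio would not raise an alarm, the excess even under a forced negative binomial would be at most about 12%, and mortality also has a Kaplan-Meier analysis.
- **That the plan requires the swap.** It permits it.

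The concern is therefore mainly about place of death, a secondary outcome.

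**What to change.** Split the Proportions row of Table 6.

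- **Bed-day proportions:** keep the binomial model with quasi-binomial as the alternative, and estimate the dispersion from Pearson chi-square over degrees of freedom.
- **Place of death and death:** logistic (binomial) regression only. Delete the quasi-binomial and negative binomial alternatives and the over-dispersion (deviance/df) diagnostic, and judge fit by calibration.
- **Repeated controls:** if the same control patient is matched more than once, use standard errors clustered on the patient for these outcomes.

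This is a two-row edit to the table. It needs no new data and almost no extra analysis, since the binomial model is already the initial model. Where results already exist, the same purpose is served by confirming from the technical appendix that the logistic fits are the ones relied on for these two outcomes.
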